Date	11/13/2019
Title	Clinical Utility of Postoperative Hemoglobin Testing Following Vaginal Hysterectomy and Reconstruction for Symptomatic Pelvic Organ Prolapse
Principle Investigator	[name]
Sub-Investigators	[name]
Research Specialist	[name], MS
Department	Urogynecology
Hatton #	19-111

Introduction:

- Obtaining a complete blood count (CBC) on post-operative day (POD) 1 to assess postoperative hemoglobin levels is routine practice at our institution after pelvic reconstructive surgery.
- There is minimal data supporting this practice. Multiple studies throughout the gynecology literature suggest that this is not a necessary or cost effective strategy to assess for postoperative anemia. ^{2,6,9,11}
- Most patients who require blood transfusion or reoperation for bleeding will show clinical signs of anemia. ^{2, 6, 7, 11} It is necessary to consider the entire clinical picture before initiating blood transfusion for postoperative anemia. ¹
- Although the individual cost of each lab test is low, the cumulative cost of these tests is substantial. ^{2,9}
- The procedure of choice for prolapse repair by Cincinnati Urogynecology Associates, TriHealth Inc. is a vaginal hysterectomy (TVH) with concurrent apical, anterior, and posterior compartment native tissue repairs as indicated. A review of the literature failed to identify any studies that have looked specifically at the utility of postoperative CBC after vaginal hysterectomy with prolapse repairs.

Purpose of Study

- To determine if checking a routine CBC results in clinically relevant changes to patient care in women undergoing pelvic reconstructive surgery with vaginal hysterectomy for treatment of pelvic organ prolapse.

Hypothesis or Research Question:

- We hypothesize that there is minimal utility in the routine collection of POD1 CBC in patients undergoing TVH during vaginal prolapse repairs.
- We also hypothesize that the overall blood transfusion rate of our pelvic reconstructive patients is low, and that a more selective approach to CBC collection would be appropriate.

Background:

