Surgeons commonly check a CBC on patients after major gynecologic surgery. This is done to evaluate for postoperative anemia and to provide surgeon reassurance prior to discharging a patient home. There are more than 200,000 inpatient operative procedures completed for pelvic organ prolapse annually in the United States.⁵ Studies quote rates from, 87-99.6% of patients having a CBC drawn on POD1 and up to 1/3 of these patients requiring some intervention based on these results.^{6,7,11} Further evaluations of abnormal lab results may be additional blood work or more invasive procedures such as imaging tests or reoperation.

In recent years, multiple studies have shown that routine preoperative lab testing is not ubiquitously indicated for women undergoing gynecologic and urologic surgery. Thirty day outcomes do not change regardless of lab collection prior to surgery.³ The American Society of Anesthesia recommends against routine preoperative lab testing in the absence of clinical indications.¹⁴ Even with these recommendations, up to 40% of women receive un-indicated preoperative lab testing prior to urologic procedures.¹³ Similar to lab testing in the preoperative period, despite the high rate surgeons ordering postoperative labs, the clinical utility of a POD1 CBC has been called into question.

Throughout the gynecology literature, studies have identified multiple risk factors for a larger drop in hemoglobin on POD1 including hysterectomy at the time of pelvic surgery, midurethral sling placement at the time of prolapse repair, lower BMI, and the amount of IVF received in the OR.^{2,11} These findings were corroborated by additional studies, which also identified preoperative anemia, history of coagulopathy, and African American or Hispanic ethnicity as risk factors for postop blood transfusion.^{4,8,10,12} Although these patient and surgical characteristics have been identified as risk factors for postoperative anemia and transfusion, one study noted based on their data, that if they restricted CBC collection to patients with at 2 or more signs of anemia on POD1, 90% of their sample would not have required testing.⁷ Other studies have corroborated that almost all patients that ultimately require blood transfusion will show clinical signs of anemia.^{2,6,11}

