Within our Division, the surgical procedure of choice to treat pelvic organ prolapse is a total vaginal hysterectomy with concurrent vaginal native tissue prolapse repairs. As standard practice, patients are kept overnight in the hospital for observation and a CBC is collected the morning on POD1. Studies in the gynecology literature have looked at the utility of routine CBC on patients after elective gynecologic surgery in general, total laparoscopic hysterectomy, minimally invasive sacrocolpopexy with or without concurrent hysterectomy, but none have looked specifically at our patient population having a vaginal hysterectomy with vaginal prolapse repairs.^{2,6,7,10}

Our goal is to show that routine collection of a CBC on POD1 in asymptomatic patients after vaginal hysterectomy with prolapse repair is unnecessary. If this is found, we could stop routine CBC collection which is a bothersome procedure for many patients and an added expense contributing to high health care costs.

Research Plan:

Study Design: Retrospective chart review

Setting of Study: TriHealth Epic platform at one of the various clinical locations.

Participants: All patients who underwent a total vaginal hysterectomy with concurrent vaginal native tissue prolapse repairs performed by one of four fellowship trained urogynecologists at TriHealth between 10/1/2014 and 10/1/2019. The patients will be identified by CPT codes in the EPIC electronic medical record.

Inclusion Criteria:

Total vaginal hysterectomy with or without bilateral salpingectomy/oophorectomy (CPT 58260, 58262, 58263, 58270, 58290, 58291, 58292, 58294)

At least one of the following vaginal native tissue prolapse repairs

Apical repair with uterosacral ligament suspension (CPT 57283)

Apical repair with sacrospinous ligament fixation (CPT 57282)

Anterior repair (CPT 57240, 57260, 57284, 57285, 57250)

Posterior repair (CPT 45560, 56800, 56810, 57200, 57210, 57250)

Age >18

Surgery by one of four fellowship trained urogynecologists at TriHealth

Exclusion Criteria:

Concomitant surgical procedure by a second surgeon

Malignancy identified at the time of surgery or active malignancy

Cases converted to open hysterectomy or prolapse repairs

Prolapse repair completed robotically

Prolapse repair completed with mesh

Known coagulopathy

Patient on long term preoperative anticoagulant medication (Arixtra, Coumadin, Eliquis, Heparin, Lovenox, Pradaxa, Savaysa, Xarelto)

Sample Size:

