Similar retrospective studies included between 629-1105 patients in their chart review.^{2, 6, 7, 11} Based on the number of vaginal hysterectomies performed by our department annually, we anticipate five years of data collection will provide a comparable study size for this review. Our anticipated sample size will be approximately 800 patients.

Data Collection: Please see attached data collection sheet

- Charts of all patients having a total vaginal hysterectomy by one of our four fellowship trained urogynecologists during the study time frame will be identified and analyzed for inclusion and exclusion criteria.
- All charts meeting inclusion criteria will be included in the analysis.
- Each chart will be reviewed and the following variables collected for analysis:
 - Type(s) of prolapse repair(s)
 - Additional procedure for urinary incontinence at the same time as hysterectomy and prolapse repair – yes/no
 - Preoperative CBC collected within 30 days of surgery – yes/no
 - Preoperative hemoglobin
 - CBC collected the morning of POD1 – yes/no
 - POD1 hemoglobin
 - Change in hemoglobin from preoperative to postoperative collection
 - Change in hemoglobin level ≥ 2 – yes/no
 - Postoperative hemoglobin ≤ 10 – yes/no
 - More than one postoperative hemoglobin obtained – yes/no
 - Patient with objective signs of anemia (*persistent hemodynamic changes: pulse >100 beats per minute, blood pressure <90/60*) – yes/no
 - Patient with subjective signs of anemia (*dizziness, lightheadedness, weakness, pale, cool, diaphoretic*) – yes/no
 - Blood transfusion – yes/no
 - Estimated blood loss
 - IVF volume received intraoperatively
 - Length of surgery (in minutes)
 - Prophylactic heparin given preoperatively – yes/no
 - General demographic data including: name, DOB, age, race, BMI, medical comorbidities, parity, smoking history, menopausal status
 - Preoperative aspirin use – yes/no
 - Preoperative antiplatelet medication use (i.e.: Brilinta, Effient, Plavix) – yes/no
 - Stage of pelvic organ prolapse at preoperative appointment
 - Prior abdominal or pelvic surgery – yes/no
 - Patient readmitted within 30 days of surgery – yes/no

- Patient seen in emergency department within 30 days of surgery – yes/no
- Length of hospital stay (in days)
- Delay in discharge due to CBC results – yes/no

Intervention or experimental aspect of the study:

- No intervention will occur as part of this study.

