- There are no potential risks to the study population by any aspect of this study.

Statistical Analysis:

Demographic data will be described using frequency (percentage) for categorical variables and mean (standard deviation) or median (min, max) for continuous variables. The percentage of subjects with hemoglobin less than 10 g/dL at POD1 will be evaluated as well as the percentage of subjects with signs of anemia. Pearson product moment correlation coefficient will be employed to measure the association between postoperative hemoglobin level and perioperative variables such as age, BMI, blood loss, or length of surgery. The mean hemoglobin change from pre- to postoperative measurement in symptomatic subjects will be compared with that of asymptomatic subjects using Student's t-test. Multiple linear regression will be used to investigate risk factors impacting mean decrease in hemoglobin. On the other hand, multiple logistic regression will be used to investigate factors associated with the presence of signs of anemia.

Ethical Considerations:**Informed Consent:**

- Informed consent will not be required given the retrospective chart review design of this study.

Privacy Information:

- Extensive effort will be made to ensure and maintain participant confidentiality. All identifying information will be maintained in a secure area at all times. All communication between staff members regarding participant data will occur via the Subject ID number only. However, identifying information will be retained in the original/source documents.
- The Excel spreadsheet will be stored on a password protected, encrypted TriHealth computer for ten years following study closure, and then purged.

Cost/Budget:

- This study will incur no cost to the institution, the participants, or the investigators.

Estimated Period of Time to Complete Study	
When will study begin?	Winter 2019
Protocol Development Completed	2 weeks
Admin Review Time	2 weeks
IRB Approval	3 weeks
Data Collection	4 weeks
Data Analysis	2 weeks
Presentation Development (if applicable)	2 weeks
Manuscript Development (if applicable)	4 weeks
Journal Submission Process (if applicable)	4 weeks
Study Closure	2 weeks

When and how will results be disseminated?

- The results will be disseminated by way of an oral or poster presentation at a national meeting and with publication in a high-impact journal.

References:

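### The planned analyses do not show what the POD1 CBC finds or changes in women without signs of anemia, which is what the goal requires

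*Combined protocol and SAP*

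**What the plan says.** The aim is stated at the end of the Background: "Our goal is to show that routine collection of a CBC on POD1 in asymptomatic patients after vaginal hysterectomy with prolapse repair is unnecessary". The Hypothesis section adds that "a more selective approach to CBC collection would be appropriate", and the Purpose of Study asks whether the routine CBC leads to clinically relevant changes in care.

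The Statistical Analysis section then plans:

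- two overall percentages: "hemoglobin less than 10 g/dL at POD1 will be evaluated as well as the percentage of subjects with signs of anemia";
- correlations (Pearson) of postoperative hemoglobin with perioperative variables such as age, BMI, blood loss and length of surgery;
- a comparison of means: "The mean hemoglobin change from pre- to postoperative measurement in symptomatic subjects will be compared with that of asymptomatic subjects using Student's t-test";
- a linear regression for the mean decrease in hemoglobin, and a logistic regression for the presence of signs. Neither names the other variable as a factor.

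The Data Collection list includes, for each patient, POD1 hemoglobin, flags for hemoglobin ≤ 10 and change ≥ 2, objective signs, subjective signs, transfusion, more than one postoperative hemoglobin, delay in discharge due to the CBC, readmission and emergency visit. The Statistical Analysis section names no analysis of the last five.

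**The concern.** The claim to be supported concerns a subgroup: in women without signs, the CBC adds nothing that matters. It needs a count within that subgroup: how many asymptomatic women had their care changed and, behind that, how many had a low value. The plan gives the overall frequency of low hemoglobin, the overall frequency of signs, and a difference in means. None of these is that count.

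The stake is the practice change that the Background describes, stopping routine collection. Followed exactly, the plan could report a clear difference in mean change between symptomatic and asymptomatic women while leaving open whether few or many asymptomatic women had a low result, and whether any of them was managed differently because of it.

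**Working it through.** **Inputs.** The documents give N ("Our anticipated sample size will be approximately 800 patients"), the hemoglobin cut-off of 10 and the change threshold of 2. They give no expected rate of low hemoglobin or of signs, and no mean or SD, so those below are assumptions shown over a range. The plan states no yield in asymptomatic women to reproduce. The 800 rests on similar studies (629 to 1105 patients) and department volume, without a precision target.

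**Step 1: what the two percentages allow.** Let L be the number with low hemoglobin and S the number with signs. With only L, S and N known, the number with low hemoglobin and no signs lies between max(0, L − S) and min(L, N − S). Sensitivity of signs for low hemoglobin is 1 minus that number divided by L.

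| Assumed low Hb | Assumed signs | L | S | No signs | Low Hb, no signs | % of no-sign women | Sensitivity |
|---|---|---|---|---|---|---|---|
| 15% | 10% | 120 | 80 | 720 | 40 to 120 | 5.6 to 16.7 | 67% to 0% |
| 15% | 30% | 120 | 240 | 560 | 0 to 120 | 0 to 21.4 | 100% to 0% |
| 5% | 10% | 40 | 80 | 720 | 0 to 40 | 0 to 5.6 | 100% to 0% |
| 10% | 10% | 80 | 80 | 720 | 0 to 80 | 0 to 11.1 | 100% to 0% |
| 20% | 10% | 160 | 80 | 720 | 80 to 160 | 11.1 to 22.2 | 50% to 0% |
| 30% | 20% | 240 | 160 | 640 | 80 to 240 | 12.5 to 37.5 | 67% to 0% |

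For the first row: 120 − 80 = 40 and min(120, 720) = 120; 40/720 = 5.6% and 120/720 = 16.7%. The end points move with the assumed rates, but every row leaves the count wide open.

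**Step 2: whether the t-test closes the gap.** Assume mean drops of 2.0 v 1.7 g/dL, SD 1.0, in 80 v 720 women. The standard error is 1.0 × √(1/80 + 1/720) = 0.118, so t = 0.3/0.118 = 2.55 and p = 0.011. Under a normal distribution and the protocol's own threshold of 2, 50% of 80 = 40 symptomatic women and 38.2% of 720 = 275 asymptomatic women reach it. Signs then identify 40/315 = 13% of such drops although the test is significant.

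The mean does not fix the tail either. With an assumed mean POD1 hemoglobin of 11.5 g/dL in 720 asymptomatic women, the expected number below 10 is 720 × Φ((10 − 11.5)/SD): about 22, 76 or 126 for SD 0.8, 1.2 or 1.6. The planned test is also on change, not on the POD1 level.

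**Step 3: whether the regressions close it.** One models mean decrease and the other models signs. Even if hemoglobin were entered in the second, an odds ratio is not a count of asymptomatic women.

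**Step 4: what a cross-tabulation would give.** With 720 asymptomatic women (assumed), exact 95% intervals are:

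- 0 with the outcome: 0%, upper limit 1 − 0.025^(1/720) = 0.51%;
- 5 with the outcome: 0.69% (0.23% to 1.61%);
- 36 with the outcome: 5.0% (3.5% to 6.9%).

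The yield in asymptomatic women would therefore be estimated closely. Sensitivity for a rare outcome would not: if 8 women were transfused (1%, assumed) and all 8 had signs, the lower limit is 0.025^(1/8) = 63%.

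**The case against.** The strongest objection is that low hemoglobin is the wrong target. The purpose is change in care, and the Introduction asks for the whole clinical picture before transfusion. An asymptomatic woman with a value below 10 whose care does not change is the kind of result that the study suspects to be useless. This stands, and it decides the order of the fix: change in care first, laboratory values second. A reader might infer that every asymptomatic woman with a low value is a case that selective testing would miss; the stated purpose does not support that.

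Second, all the variables are listed for collection, and the investigators could tabulate them anyway. That is true. A reader might infer that the study cannot answer its question, but the gap lies in the written analyses, not in the data. The logistic model's factors are also unlisted and could include hemoglobin, though that would still not yield the count.

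Third, the rates are not the trial's. A reader might take 10% with signs from the Background, where a cited study reports that "90% of their sample would not have required testing". That figure belongs to another sample and to a rule of two or more signs, whereas the Data Collection list records objective and subjective signs as separate yes/no items with no such rule. Here 10% is only an assumption. The mean drops and SDs in step 2 were likewise chosen for illustration; they show that a significant test can coexist with poor identification, not that it will.

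Finally, a reader might infer that either t-test result would be presented as support for the hypothesis. No section says how the test will be interpreted, so that inference has no basis in the documents.

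**Conclusion.** The concern holds for the analyses as written. They give two uncrossed percentages, a comparison of mean change and two regressions, and none reports what the CBC found or changed in asymptomatic women. The size of the gap depends on rates that the documents do not give. At 800 women and 15% low hemoglobin, the number of asymptomatic women with a low value could be 40 to 120 if 10% have signs, or 0 to 120 if 30% do. That the percentages leave this count open holds in every row of the table; the particular end points do not carry over. Nothing here shows that signs perform badly or that the hypothesis is wrong, only that the planned output could not tell. Because the conclusion is meant to support a change of practice in exactly this subgroup, the plan should be amended before the analysis.

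**What to change.** In the Statistical Analysis section:

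1. Make the main analysis a cross-tabulation by sign status (any, objective, subjective) of the change-in-care outcomes already collected: transfusion, repeat hemoglobin, and delay in discharge due to the CBC. Show readmission and emergency visit within 30 days alongside.
2. As secondary, cross-tabulate sign status against low hemoglobin and against change ≥ 2. Use one cut-off for low hemoglobin: Data Collection has ≤ 10 and Statistical Analysis has less than 10, and the two must be reconciled.
3. Define symptomatic, which the Statistical Analysis section leaves open.
4. Among women with a POD1 CBC, report the number and percentage of asymptomatic women with each outcome, and the sensitivity and negative predictive value of signs, all with exact 95% confidence intervals. Note that sensitivity for rare outcomes will be imprecise.
5. Keep the t-test as supportive.

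The cost is a few sentences and one extra table, with no new data. The downside for the investigators is that the result may be less favourable to the hypothesis.

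### Compare hemoglobin change between symptomatic and asymptomatic subjects with Welch's t-test instead of Student's: a cheap safeguard in a secondary analysis

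*Combined protocol and SAP*

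**What the plan says.** The Statistical Analysis section sets out three analyses of hemoglobin that bear on this point.

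- Correlation: "Pearson product moment correlation coefficient will be employed to measure the association between postoperative hemoglobin level and perioperative variables". The outcome is the postoperative level. The list of variables is open, with four named as examples.
- Group comparison: mean pre-to-postoperative change "in symptomatic subjects will be compared with that of asymptomatic subjects using Student's t-test". The outcome is change. Unequal variances are not mentioned.
- Regression: "Multiple linear regression will be used to investigate risk factors impacting mean decrease in hemoglobin". The outcome is again change.

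The level also has a descriptive use of its own: "The percentage of subjects with hemoglobin less than 10 g/dL at POD1 will be evaluated".

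Under Data Collection, the plan records "Change in hemoglobin from preoperative to postoperative collection". It also records whether there was a "Preoperative CBC collected within 30 days of surgery", so change may be missing for some patients. Objective and subjective signs of anemia are each recorded yes/no. The Sample Size section anticipates about 800 patients. No alpha, hemoglobin SD or expected share of symptomatic patients is stated.

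**The concern.** Student's t-test estimates one common variance from both groups. When the groups are of unequal size, the larger one dominates that estimate. If the smaller group is in truth more variable, the standard error of the difference is too small and the test rejects too often. If the smaller group is less variable, the test rejects too rarely. With equal sizes or equal SDs the problem disappears.

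Symptom status is observed, not allocated, so nothing in the design makes the groups equal in size or in spread. At stake is the calibration of one p-value and its confidence interval, for the contrast that shows whether symptomatic patients lose more hemoglobin. The stated purpose, whether a routine CBC changes care, does not rest on this contrast.

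**Working it through.** The plan has no figure of its own to reproduce here. The check asks how far Student's test departs from its nominal level under stated assumptions.

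**Inputs**

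- Total N = 800, from Sample Size. The calculation assumes that every patient has both hemoglobin values.
- Two-sided alpha of 5%: assumed, as the documents state none.
- Group split: not given for this cohort. The only hint is in Background, from a cited sacrocolpopexy study: had testing been restricted to "patients with at 2 or more signs of anemia on POD1, 90% of their sample would not have required testing". Carried over, 10% of 800 = 80, hence 80 versus 720. That is a different operation and a two-sign rule. The signs recorded here carry no two-sign minimum, so the symptomatic group could be larger. Splits up to 400 versus 400 are therefore shown.
- SD ratio k (symptomatic/asymptomatic): not given; assumed 0.75 to 1.5.

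**Formulas** (asymptomatic SD = 1, n1 symptomatic, n2 asymptomatic)

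- Pooled variance = [(n1 − 1)k² + (n2 − 1)] / (n1 + n2 − 2)
- SE_pooled = √[pooled variance × (1/n1 + 1/n2)]
- SE_true = √(k²/n1 + 1/n2)
- Type I error ≈ 2Φ(−1.96 × SE_pooled/SE_true)

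**Worked case: 80 versus 720, k = 1.5**

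- Pooled variance = (79 × 2.25 + 719)/798 = 1.1237
- SE_pooled = √[1.1237 × (1/80 + 1/720)] = 0.1249
- SE_true = √(2.25/80 + 1/720) = 0.1718
- Ratio = 0.727; type I error = 2Φ(−1.425) = 15.4%

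At k = 0.75 the ratio is 0.1153/0.0918 = 1.256, which gives 1.4%.

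**Type I error of Student's test**

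| Split | k = 0.75 | k = 1 | k = 1.25 | k = 1.5 |
|---|---|---|---|---|
| 80 vs 720 | 1.4% | 5.0% | 10.1% | 15.4% |
| 160 vs 640 | 2.0% | 5.0% | 8.6% | 12.1% |
| 240 vs 560 | 2.8% | 5.0% | 7.3% | 9.3% |
| 400 vs 400 | 5.0% | 5.0% | 5.0% | 5.0% |

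Coverage of the 95% CI at 80 versus 720 is the complement: 98.6%, 95.0%, 89.9% and 84.6%. Simulation of the same row (200,000 runs) gave 1.4%, 5.0%, 10.0% and 15.3% for Student's test. Welch's test gave 4.9% to 5.1% over all 16 cells.

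**Price of Welch's test when the SDs are equal** (noncentral t)

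- 80 vs 720, difference of 0.33 SD: 79.2% power against 79.9% for Student's test (Welch degrees of freedom 97.4 against 798).
- 160 vs 640, same difference: 96.1% against 96.2%.
- 40 vs 760, difference of 0.4 SD (40,000 simulated runs): 67.1% against 69.0%. The cost approaches 2 points only when the symptomatic group is very small.

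**The case against.** The strongest reply is that naming Student's t-test is not an error on these documents. Miscalibration needs unequal sizes and unequal SDs together, and the plan gives neither. The 80 versus 720 split is borrowed from another operation and another symptom rule. With equal SDs or equal groups, Student's test is exact or nearly so. An analyst might also use the name loosely and apply an unequal-variance version. All of this stands, and it limits the point to an improvement. It does not remove the reason for the change: the method has to be named before the SDs and split are known, and Welch's test is sound in every case examined.

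A reader might also infer that the correlations are at fault, because postoperative level equals preoperative level minus the drop and so mixes baseline with loss. The documents do not support treating that as a defect. The plan labels the correlations as describing level, and level is a legitimate outcome. It nowhere says they will be read as loss, and it assigns risk factors for loss to the multiple linear regression. Nor is a level correlation empty of information on loss: for a variable unrelated to preoperative hemoglobin it points the right way, though attenuated. Extra correlations with change, or adjusted for baseline, would turn 4 coefficients into 12 for the four named variables and would largely repeat the regression.

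**Conclusion.** The point holds as an optional, low-cost improvement to one secondary comparison. Under an assumed 80 versus 720 split and SD ratios of 0.75 to 1.5, Student's test has a type I error of about 1.4% to 15% where 5% is intended. The distortion shrinks as the groups approach equal size and vanishes at 400 versus 400. Welch's test holds close to 5% throughout.

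The size rests entirely on assumed SD ratios, an assumed split, a 5% two-sided level and complete hemoglobin data in 800 patients. A reader might take the upper figures as evidence that the planned p-value will be wrong. The documents do not show that: without an SD or a symptomatic share for this cohort, even the direction of any error is unknown.

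**What to change.** In Statistical Analysis, replace the t-test sentence with:

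*Mean hemoglobin change in symptomatic and asymptomatic subjects will be compared with Welch's t-test, reporting the mean difference and 95% CI.*

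Leave the correlation sentence and the regression as they are.

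The cost is one sentence of wording and no new data. The same patients enter the comparison, namely those with both a preoperative and a POD1 hemoglobin. If the SDs turn out equal, the loss is 0.7 percentage points of power at 80 versus 720 for a 0.33 SD difference (79.9 − 79.2), and close to 2 points if only about 40 patients are symptomatic (69.0 − 67.1 = 1.9, for a 0.4 SD difference).

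### Student's t-test for hemoglobin change assumes equal variances that sign-defined groups need not have; Welch's test is the safer choice at little cost (minor, supporting analysis)

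*Combined protocol and SAP*

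**What the plan says.** The comparison has one sentence in the Statistical Analysis section: "The mean hemoglobin change from pre- to postoperative measurement in symptomatic subjects will be compared with that of asymptomatic subjects using Student's t-test". The document does not mention an unequal-variance form, a variance check, robust standard errors or a nonparametric alternative. The section states no alpha, sidedness, confidence level or SD.

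The groups come from two yes/no chart items under Data Collection. One is "Patient with objective signs of anemia", explained as "persistent hemodynamic changes: pulse >100 beats per minute" plus a blood pressure limit. The other is subjective signs: "dizziness, lightheadedness, weakness, pale, cool, diaphoretic". The analysis section does not say whether a symptomatic subject has objective signs, subjective signs or either.

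Under Sample Size: "Our anticipated sample size will be approximately 800 patients". No symptomatic share is given. The only clue is in the Background: in one cited study, limiting testing to patients with two or more signs would have spared 90% of the sample. That implies about 10% with two or more signs, which is one study's share under one particular rule.

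**The concern.** Student's t-test estimates one common variance. When group sizes and variances both differ, its standard error is wrong, and a larger sample does not correct it. If the smaller group is the more variable one, the standard error is too small; if the smaller group is the less variable one, it is too large.

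Allocation does not protect this comparison, because chart findings decide who falls in which group. The plan's own premises also give a reason to expect wider spread among symptomatic patients. The Introduction states: "Most patients who require blood transfusion or reoperation for bleeding will show clinical signs of anemia". Large drops should therefore gather in that group. The subjective list also includes dizziness and weakness, which patients with an ordinary drop may have (an assumption). A group that mixes large and ordinary drops has a larger SD than a group of ordinary drops alone.

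This is the only two-group test named in the plan, and it bears on whether recorded signs track the fall in hemoglobin. What is at stake is the accuracy of that p-value and of any interval built on the same standard error. The percentages with hemoglobin below 10 g/dL and with signs of anemia are not affected.

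**Working it through.** The plan states no power, alpha or SD, so there is no figure of its own to reproduce.

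**Inputs**
- Total N = 800: Sample Size section.
- Two-sided 5% level (95% interval): assumption.
- Splits: assumptions. 80 vs 720 follows the 10% clue in the Background; 264 vs 536 (33%) is a less unbalanced illustration.
- SD of the change in asymptomatic patients set to 1. Symptomatic to asymptomatic SD ratio r: assumption.

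**Step 1. SD ratio from the mixing mechanism.** Let a fraction p of symptomatic patients have a drop d = 2 SD larger, and let the rest resemble the asymptomatic. Then r² = 1 + p(1 − p)d².
- p = 0.1: 1 + 0.09 × 4 = 1.36, r = 1.17
- p = 0.2: 1 + 0.16 × 4 = 1.64, r = 1.28
- p = 0.3: 1 + 0.21 × 4 = 1.84, r = 1.36

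**Step 2. Error in the pooled standard error.** The ratio of pooled to true standard error is f = √[Vp(1/n1 + 1/n2) / (r²/n1 + 1/n2)], with Vp = [(n1 − 1)r² + (n2 − 1)]/(n1 + n2 − 2). The miss rate of a nominal 95% interval is about 2[1 − Φ(1.96f)].

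For 80 vs 720 with p = 0.1:
- Vp = (79 × 1.36 + 719)/798 = 1.036
- Pooled squared SE = 1.036 × (1/80 + 1/720) = 0.01438
- True squared SE = 1.36/80 + 1/720 = 0.01839
- f = √(0.01438/0.01839) = 0.884
- Miss rate = 2[1 − Φ(1.733)] = 0.083

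**Step 3. Miss rates for p = 0.1 / 0.2 / 0.3**

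| Split | Pooled, formula | Pooled, simulation | Welch, simulation |
|---|---|---|---|
| 80 vs 720 | 8.3% / 10.7% / 12.4% | 8.4% / 10.5% / 12.6% | 4.9–5.2% |
| 264 vs 536 | 6.3% / 7.1% / 7.6% | 6.5% / 7.1% / 7.6% | 4.9–5.2% |

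The simulation used 20,000 replicates per cell.

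**Step 4. Wider range of SD ratios, with the means assumed equal.** These are type I error rates of Student's test from the same formula at N = 800.

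| Split | r = 0.67 | 1 | 1.25 | 1.5 | 2 |
|---|---|---|---|---|---|
| 80 vs 720 | 0.7% | 5% | 10.1% | 15.4% | 24.6% |
| 264 vs 536 | 2.6% | 5% | 6.9% | 8.6% | 11.1% |
| 400 vs 400 | 5% | 5% | 5% | 5% | 5% |

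For fixed shares, the rates are almost the same at N = 629 and N = 1105, the range that the plan quotes for similar studies. When the symptomatic group is the less variable one, power is lost: at r = 0.67, 80 vs 720 and a 0.35 SD difference, it is 93% with Student's and 99% with Welch.

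**The case against.** **The name may be loose.** The word pooled does not appear in the document, and in a one-paragraph plan for a chart review Student's may simply mean a two-sample t-test. That is possible. The standard meaning is still the equal-variance test, and one sentence would settle it.

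**No error is shown.** Neither the split nor either SD is known, and with equal SDs or equal groups nothing is wrong. This stands: the point is conditional.

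**The large figures do not follow from the mechanism.** A reader might infer from Step 4 that the false-positive rate will be 15% to 25%. The documents do not support that. Those rates need SD ratios of 1.5 to 2 with equal means. The mixing mechanism with a 2 SD larger drop gives 1.17 to 1.36, and it shifts the symptomatic mean by p × d = 0.2 to 0.6 SD. The null is then false, so type I error is not the right measure; interval coverage is. The plan announces no interval, although the standard error behind the test is the same.

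**There is no stated level.** A reader might also infer that the p-value departs from the plan's own alpha. The plan states none, and the 5% here is an assumption.

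**Little rests on this test.** No primary endpoint or decision rule depends on it, which keeps the severity low.

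**The same sentence has another gap.** Symptomatic is not defined for this test, and changing the test does not cure that. It must be settled before the group sizes mean anything.

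**Conclusion.** The point holds as a minor one. The plan names a test that assumes equal variances, for groups whose sizes and spreads are set by chart findings, and it makes no allowance for a difference.

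The size depends on the assumed 5% level, split and SDs. Under the mixing mechanism, non-coverage is about 8% to 13% at 80 vs 720 and about 6% to 8% at 264 vs 536, against about 5% with Welch. Larger SD ratios would be worse. A smaller SD in a smaller symptomatic group would make the test conservative. Which case applies cannot be told from the documents.

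The case for changing the test is that equal variance cannot be presumed and the alternative costs little. It is not that an inflated error rate has been shown, nor that the study's descriptive conclusions are at risk.

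**What to change.** In the Statistical Analysis section, replace Student's t-test with a two-sided Welch t-test for this comparison. Report n, mean and SD of the hemoglobin change in each group, and the mean difference with its Welch 95% CI. State in the same sentence which recorded signs make a subject symptomatic, so that the reported groups are defined.

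This needs no new data. The cost, if the SDs are in fact equal, is a small loss of power (Student's vs Welch, N = 800):

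| Symptomatic vs asymptomatic | Assumed difference | Student's | Welch |
|---|---|---|---|
| 160 vs 640 | 0.25 SD | 0.807 | 0.805 |
| 80 vs 720 | 0.35 SD | 0.843 | 0.836 |
| 40 vs 760 | 0.46 SD | 0.808 | 0.791 |
| 20 vs 780 | 0.65 SD | 0.817 | 0.778 |

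That is under 1 point with 80 or more symptomatic patients, about 2 points with 40 and about 4 with 20. With skewed changes (skewness 1), Welch's simulated error rate is 4.9% to 5.5% with 80 or more symptomatic patients and at most 5.8% with 40.
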